## 2.4. Statistical Hypotheses

This single arm study is a study with an aim of an estimation. The primary objective of this study is to evaluate the initial anemia correction of GSK1278863 in HD patients not

using ESAs. There will be no hypothesis testing performed in this study. Two-sided 95% confidence intervals will be used for efficacy estimation.

## 3. PLANNED ANALYSES

## 3.1. Interim Analyses

No interim analysis is planned.

## 3.2. Final Analyses

The final planned primary analyses will be performed after the completion of the following sequential steps:

- 1. All subjects have completed the study as defined in the protocol.
- 2. All required database cleaning activities have been completed and final database release and database freeze has been declared by Data Management.
- 3. All criteria for releasing the randomization codes have been met.
- 4. Randomization codes have been distributed according to RandAll NG procedures.

## 4. ANALYSIS POPULATIONS

Population	Definition / Criteria	Analyses Evaluated
All Screening	
 
Consists of all subjects who are given subject number and are corrected data at screening.
 
	Study Population
Enrolled	
 
Consist of subjects in 'All Screening' except for screen failure (who never passed screening even if rescreened).
 
	
 
Study Population (some displays for EudraCT)
 

Assigned	
 
Consist of all subjects who are given randomization number regardless of whether they actually receive GSK1278863.
 
	
 
Study Population
 

All Treated Subjects	
 
Consist of all subjects who received at least one dose of GSK1278863.
 
	

Study Population

Efficacy

Safety

РК	
 
Consist of all subjects who received GSK1278863 with the PK samples collected and analyzed.
 
	• PK

NOTES :

• Basically, enrolled population will be the same as assigned population because a subject is going to be given randomized number as soon as passed screening

• Please refer to Appendix 14: List of Data Displays which details the population to be used for each displays being generated.

## 4.1. Protocol Deviations

- Important protocol deviations (including deviations related to study inclusion/exclusion criteria, conduct of the trial, patient management or patient assessment) will be summarised and listed.
- A separate summary and listing of all inclusion/exclusion criteria deviations will also be provided. This summary will be based on data as recorded on the inclusion/exclusion page of the eCRF.
- Protocol deviations will be tracked by the study team throughout the conduct of the study in accordance with the Protocol Deviation Management Plan.
  - Data will be reviewed prior to freezing the database to ensure all important deviations and deviations which may lead to exclusion from the analysis are captured and categorized on the protocol deviations dataset.
  - This dataset will be the basis for the summaries and listings of protocol deviations.

## 5. CONSIDERATIONS FOR DATA ANALYSES AND DATA HANDLING CONVENTIONS

Table 1 provides an overview of appendices within the RAP for outlining general considerations for data analyses and data handling conventions.

Section	Component
10.1	Appendix 1: Protocol Deviation Management and Definitions for Per Protocol Population
10.2	Appendix 2: Time & Events
10.3	Appendix 3: Assessment Windows
10.4	Appendix 4: Treatment States and Phases
10.5	Appendix 5: Data Display Standards & Handling Conventions
10.6	Appendix 6: Derived and Transformed Data
10.7	Appendix 7: Premature Withdrawals & Handling of Missing Data
10.8	Appendix 8: Values of Potential Clinical Importance
10.9	Appendix 9: Multicenter Studies
10.10	Appendix 10: Examination of Covariates, Subgroups & Other Strata
10.11	Appendix 11: Multiple Comparisons & Multiplicity
10.12	Appendix 12: Model Checking and Diagnostics for Statistical Analyses.

Table 1Overview of Appendices

## 6. STUDY POPULATION ANALYSES

## 6.1. Overview of Planned Analyses

The study population analyses will be based on the All Treated Subjects population, unless otherwise specified.

Table 2 provides an overview of the planned study population analyses, with full details of data displays being presented in Appendix 14: List of Data Displays.

 Table 2
 Overview of Planned Study Population Analyses

Endpoint / Parameter / Display Type	IV Type Population Data Displays Ge		enerated	
		Table	Figure	Listing
Subject Disposition				
Subject Status and Reason for Study Withdrawal	Assigned	Y		
Subject Status and Reason for Study Withdrawal by Dialysis Status	Assigned	Y		
Reasons for Subject Withdrawal	Assigned			Y
Treatment Status and Reasons for Discontinuation of Study Treatment	All Treated	Y		Y
Screening Status and Reasons for Screen Failure	All Screening	Y		Y
Subjects Enrolled by Country and Site ID	Enrolled	Y		
Protocol Deviations				
Important Protocol Deviations	Assigned	Y		Y
Subjects with Inclusion/Exclusion Criteria Deviations	Assigned	Y		Y
Populations Analyzed				
Study Populations	All Screening	Y		
Exclusions from Study Population	Assigned	Y		
Subjects Excluded from Any Population	Assigned			Y
Demographic and Baseline Characteristics				
Demographic Characteristics	All Treated	Y		Y
Demographic Characteristics by Dialysis Status	All Treated	Y		
Age Ranges	Enrolled	Y		
Race and Racial Combinations	All Treated	Y		Y [1]
Family History for CV Risk Factors	All Treated	Y		Y
Substance Use (History of Tobacco Use, Alcohol Intake)	All Treated	Y		Y
Prior and Concomitant Medications				
Current/Past Medical Conditions	All Treated	Y		Y
Current/Past Medical Conditions by Dialysis Status	All Treated	Y		
Concomitant Medications [2]	All Treated	Y		Y
Other Concomitant Medications [3]	All Treated	Y		Y

Endpoint / Parameter / Display Type	Population	Data Displays Generated			
		Table	Figure	Listing	
Other Concomitant Medications [3] by Dialysis Status	All Treated	Y			
Blood products and blood supportive care products [4]	All Treated	Y		Y	
Blood products and blood supportive care products [4] by Dialysis Status	All Treated	Y			
Dialysis		•			
Dialysis Status	All Treated	Y		Y	
Baseline Mode of Dialysis	All Treated	Y		Y	
Subjects with Change in Hemodialysis	All Treated			Y	
Baseline Vascular Access	All Treated	Y		Y	
Subjects with Vascular Therapeutic Procedures during the study period	All Treated			Y	
Exposure and Treatment Compliance					
Exposure to Study Treatment	All Treated	Y		Y	
Exposure to Study Treatment by Dialysis Status	All Treated	Y			
Treatment Compliance	All Treated	Y		Y	

NOTES :

• Y = Yes display generated.

• Some summaries will be generated as efficacy analyses.

[1] Listing of race.

[2] Concomitant medications in prior-therapy period, on-therapy period, and post-therapy period will be summarized separately.

[3] On-therapy ESA and iron medication will be provided.

[4] On-therapy blood products and blood supportive care products will be provided.

## 6.1.1. Planned Summary Display Details

A subject who has multiple subject numbers (i.e. rescreened subject) will be analyzed as a unique subject based on the latest screening result.

The definition of subgroup is described in Appendix 10.

#### • Subject Disposition

#### Subject Status and Reason for Study Withdrawal

The number and percentage of subjects completing the study or withdrawing early from the study will be summarized overall and by reason for withdrawal. Reasons for withdrawal will be listed for subject. The subgroup analysis for dialysis status will be summarized as the same.

#### Treatment Status and Reasons for Discontinuation of Study Treatment

The number and percentage of subjects completing the treatment or discontinuing the treatment during the study will be summarized overall and by reason.

#### Screening Status and Reasons for Screen Failure

The number and percentage of subjects who failed screening and were therefore not randomized into the study, overall and by reason, will be summarized for all screening population. Note that the reasons for rescreen subjects who initially failed but subsequently enrolled are not included in the display (see Section 10.6.2).

#### Subjects Enrolled by Country and Site ID

The number and percentage of subjects by region, country and center will be summarized.

#### • Protocol Deviations

#### Important Protocol Deviations

The number and percentage of subjects who had important protocol deviations defined in PDMP will be summarized.

#### Subjects with Inclusion/Exclusion Criteria Deviations

The number and percentage of subjects with any Inclusion/Exclusion Criteria Deviations will be summarized, further classifying inclusion/exclusion deviations.

#### • Population Analyzed

#### Study Populations

The number of subjects in each analysis population (defined in Section 4) will be summarized.

#### Exclusions from Study Population

The number of subjects excluded from All Treated Subjects population will be summarized for the assigned population.

#### • Demographic and Baseline Characteristics

#### **Demographic Characteristics**

The number and percentage of subjects or summary statistics will be provided for the demographic and baseline characteristics: Sex, Age (years), Age Group (years), Ethnicity, Race detail, Height, Weight, and Body Mass Index. Age Group (years) will be categorized into 3 ('<=18', '19-64', '>=65'). The subgroup analysis for dialysis status will be summarized as the same.

#### Age Ranges

The number and percentage of subjects within each age range category will be provided. Age range will be categorized into: Adult (18-64 years), >=65-84 years, >=85 years.

#### Race and Racial Combinations

Summaries of race and racial combinations will be provided.

#### Family History for CV Risk Factors

A summary of family (first degree relatives) history for CV risk factors will be provided.

#### Substance Use (History of Tobacco Use, Alcohol Intake)

A summary of substance use will be provided.

#### • Prior and Concomitant Medications

#### Current/Past Medical Conditions

The number and percentage of subjects with current and past medical conditions recorded in eCRF will be provided. The subgroup analysis for dialysis status will be summarized as the same.

#### **Concomitant Medications**

The number and percentage of subjects reporting the use of each concomitant medication will be summarized by anatomical therapeutic chemical (ATC) Level 1, and Ingredient. Summaries of pre-therapy, on-therapy, and post-therapy medication will be provided separately. See Section 10.4.1.3 for treatment states for concomitant medications.

#### Other concomitant medications

The similar summary as above will be provided focusing on on-therapy ESA and iron medication. See Section 10.4.1.3 for treatment states. The subgroup analysis for dialysis status will be summarized as the same.

#### Blood products and blood supportive care products

The number and percentage of subjects who use blood products and/or blood supportive care products will be provided. The details for the use will also be provided. The subgroup analysis for dialysis status will be summarized as the same.

#### • Dialysis

#### **Dialysis Status**

The number and percentage of subjects with dialysis status of newly started dialysis and maintenance dialysis will be provided. Definitions of dialysis status are described in the protocol section 5.3.

#### **Baseline Mode of Dialysis**

The number and percentage of subjects with each baseline mode of dialysis (i.e. haemodialysis, haemofiltration, or haemodiafiltration) will be provided.

#### **Baseline Vascular Access**

The number and percentage of subjects with each baseline vascular access will be provided. Previous vascular access will be summarized as the same.

#### • Exposure and Treatment Compliance

#### Exposure to Study Treatment

Full details of exposure definition are presented in Appendix 6.

Daily dose, cumulative dose, and days on study drug will be summarized using mean, standard deviation, median, minimum, and maximum. Regarding days on study drug, the number and percentage of subjects within each category (i.e. 1-28, 29-56, 57-84, 85-112, 113-140, 141-168, >168 (days)) will also be provided. The subgroup analysis for dialysis status will be summarized as the same.

#### **Treatment** Compliance

Full details of treatment compliance definition are presented in Appendix 6.

The number and percentage of subjects within each category of treatment compliance will be provided and the categories will be classified into <80%, 80% to 120%, and >120%.

#### 7. PRIMARY STATISTICAL ANALYSES

#### 7.1. **Primary Efficacy Analyses**

#### 7.1.1. **Overview of Planned Primary Efficacy Analyses**

The primary efficacy analyses will be based on the All Treated Subjects population, unless otherwise specified.

Table 3 provides an overview of the planned efficacy analyses, with full details of data displays being presented in Appendix 14: List of Data Displays.

#### Table 3 **Overview of Planned Primary Efficacy Analyses**

Endpoint / Parameter/ Display Type		Absolute						
	Stats Analysis		Summary		Individual			
	Т	F	L	Т	F	F	L	
Change from baseline in Hgb at Week 4				Y				
Number (%) of subjects by Hgb change from baseline				Y				
category at Week 4 [1]								
Change from baseline in Hgb at Week 4				Y				
by Dialysis Status								
Number (%) of subjects by Hgb change from baseline				Y				
category at Week 4 [1]								
by Dialysis Status								
NOTES								

T = Table, F = Figure, L = Listing, Y = Yes display generated.

Stats Analysis = Represents TFL related to any formal statistical analyses (i.e. modelling) conducted.

Summary = Represents TFL related to any summaries (i.e. descriptive statistics) of the observed raw data.

Individual = Represents FL related to any displays of individual subject observed raw data.

 $[1] \leq -2$ , -2 to -1, -1 to 0, 0 to 1, 1 to 2, and >2 g/dL. In addition, within  $\pm 1$  g/dL and over  $\pm 2$  g/dL.

#### 7.1.2. **Planned Efficacy Statistical Analyses**

Pri	Primary Analyses					
En	dpoint(s)					
•	Change from baseline in Hgb at Week 4					
•	Number (%) of subjects by Hgb change from baseline category at Week 4					
Мс	del Specification					
•	Hgb values from central laboratory will be used, unless otherwise specified. However, if a central laboratory Hgb value is missing, a corresponding non-missing HemoCue Hgb value will be used (See Section 10.6.3).					
•	The primary analysis is to assess modest increase in Hgb in initial response to GSK1278863 (i.e., Hgb increase by $\leq 2$ g/dL after 4 weeks of treatment), on the basis of the mean change from baseline in Hgb at Week 4 as well as the number (%) of subjects by Hgb change from baseline category at Week 4 as the primary efficacy endpoints.					

• For the change from baseline in Hgb at Week 4, the summary statistics will be calculated,

along with the two-sided 95% confidence interval based on t-distribution.

 The change in Hgb at Week 4 will be classifieds into different categories (i.e., ≤-2, >-2 to -1, >-1 to 0, >0 to 1, >1 to 2, and >2 g/dL), and the number (%) of subjects in each category will be summarized. In addition, 'within ± 1 g/dL (i.e., ≥-1 and ≤1 g/dL)' and 'over ± 2 g/dL (i.e., <-2 and >2 g/dL)' categories will be provided.

#### 7.1.3. Planned Summary Display Details

The definition of subgroup is described in Appendix 10.

#### Change from baseline in Hgb at Week 4

This summary will be included within a summary of change from baseline in Hgb at each assessment visit (See Section 8.1.2). The values will be summarized using mean, standard deviation, 95%CI, minimum, P25, median, P75, and maximum at Week 4 visit. The subgroup analysis will be summarized as the same.

#### Number (%) of subjects by Hgb change from baseline category at Week 4

The number and percentage of subjects within each category will be provided and the categories will be classified into  $\leq -2$ ,  $\geq -2$  to -1,  $\geq -1$  to 0,  $\geq 0$  to 1,  $\geq 1$  to 2, and  $\geq 2$  g/dL). In addition, 'within  $\pm 1$  g/dL (i.e.,  $\geq -1$  and  $\leq 1$ )' and 'over  $\pm 2$  g/dL (i.e.,  $\leq -2$  and  $\geq 2$ )' categories will be provided. The subgroup analysis will be summarized as the same.

## 8. SECONDARY STATISTICAL ANALYSES

## 8.1. Secondary Efficacy Analyses

## 8.1.1. Overview of Planned Secondary Efficacy Analyses

The secondary efficacy analyses will be based on the All Treated Subjects population, unless otherwise specified.

Table 4 provides an overview of the planned secondary efficacy analyses, with further details of data displays being presented in Appendix 14: List of Data Displays.

Dose level (mg) at each assessment visit			Y	Y		
by Dialysis Status			N			
>13.0 g/dL [3]			Y			
Duration (days) of treatment interruption due to Hgb			Y			
>13.0 g/dL [3]						
by Dialysis Status						
Dose adjustment			Y			
Dose adjustment			Y			
by Dialysis Status						
Number (%) of subjects with each dose level at each			Y			
assessment visit						
Number (%) of subjects with each dose level at each			Y			
assessment visit						
by Dialysis Status						
Number of dose adjustment to reach the lower Hgb target			Y			
Hgb level (10.0 g/dL)			N			
Number of dose adjustment to reach the lower Hgb target			Y			
Hgp level (10.0 g/dL)						
by Dialysis Status						
Uther				V		
Scaller plot of change from baseline in Hgb at week 4 Vs.				ľ		
Cantuluate Covariates [0]				V		
Scaller plot of mean dose vs. candidate covariates [6]		1		Υ		

NOTES :

[1] Not only within the target range, but also subjects with above and below target range will be assessed.
[2] Time to first reach the lower target Hgb level will be estimated by Kaplan-Meier method using P25, median and P75. Subjects who could not reach lower target will be regarded as censored.

Endpoint / Parameter/ Display Type			Abso	olute		
	Stats A	nalysis	Summary		Individual	
	Т	F	Т	F	F	L

[3] On-therapy Hgb values observed in scheduled visits will be included. On-therapy Hgb values observed in unscheduled visits will be included if specified (see Section 8.1.2)

[4] Based on literature review the distributions of TSAT and hepcidin are skewed and require a log-transformation.

[5] Summaries for dose adjustment will be based on HemoCue Hgb values including those of unscheduled visits.[6] Figures will include the candidate covariates of body weight and baseline Hgb, and will be produced for overall and dialysis status groups.

### 8.1.2. Planned Efficacy Table Displays

#### • Hgb

#### Hgb at each assessment visit

The values will be summarized using mean, standard deviation, 95%CI, minimum, P25, median, P75, and maximum at each assessment visit. Graphical summaries will be provided using mean and 95% CI over time. The subgroup analysis for dialysis status will be summarized as the same.

#### Change from baseline at each assessment visit

The values will be summarized using mean, standard deviation, 95%CI, minimum, P25, median, P75, and maximum at each assessment visit. Graphical summaries will be provided using mean and 95% CI over time. This will be also summarized by baseline dialysis status.

#### Number (%) of subjects with Hgb within the target range at each assessment visit

The number and percentage of subjects with Hgb within, above and below the target range at each assessment visit will be summarized. This will be also summarized by baseline dialysis status.

#### *Time (in days) to reach the lower target Hgb level (10.0 g/dL)*

The time (in days) will be summarized using P25, median, and P75 by Kaplan-Meier method. Kaplan-Meier plot of time to event will be provided using on-therapy Hgb values. Subjects who could not reach lower target will be regarded as censored. This will be also summarized by baseline dialysis status.

#### Number (%) of subjects who have an Hgb level of less than 7.5 g/dL

The number and percentage of subjects who have an Hgb level of less than 7.5 g/dL will be summarized. On-therapy Hgb values observed in both scheduled and unscheduled visits will be included in the summary. This will be also summarized by baseline dialysis status.

# Number (%) of subjects who have an Hgb increase of more than 2.0 g/dL over any 4 weeks

The number and percentage of subjects who have an Hgb increase of more than 2.0 g/dL over any 4 weeks will be summarized. On-therapy Hgb values will be used for the summary. This will be also summarized by baseline dialysis status. See Section 10.6.3 for detailed derivation.

# Number (%) of subjects who have an Hgb level of more than 13.0 g/dL and number of episodes

The number and percentage of subjects who have an Hgb level of more than 13.0 g/dL and number of episodes will be summarized. On-therapy Hgb values observed in both scheduled and unscheduled visits will be included in the summary. This will be also summarized by baseline dialysis status.

#### Scatter plot of Hgb assessments: Central Laboratory vs. HemoCue

A scatter plot of Hgb values measured by Central Laboratory versus Hgb values measured by Hemocue will be produced along with Pearson's correlation coefficient. All available pairs of Hgb (i.e. non-missing values in both from central laboratory and from the corresponding HemoCue measurement) will be used.

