6.3. Treatment Schedule

Starting dose (Day 1 to Week 4)

In the Japanese HD patients not using ESAs enrolled in the study, oral administration of GSK1278863 once daily at the starting dose of 4 mg will be started (Day 1), and continued until the day of Week 4.

Maintenance Dose (Week 4 to Week 24)

From Weeks 4 to 24, interruption of treatment or dose adjustments will be made within the maintenance dose range of 1-24 mg (Table 4) according to the dose adjustment algorithm (Table 5) to achieve and/or maintain Hgb within the target range (10.0-12.0 g/dL) based on the HemoCue Hgb value measured every 4 weeks. Dose changes will be made every 4 weeks. If any of the one-step dose reduction criteria is met during treatment at the minimum maintenance dose (1 mg), treatment should be interrupted; once the one-step dose increase criteria are met, treatment at 1 mg will be resumed. If the one-step dose increase criterion is met during treatment at the maximum maintenance dose (24 mg), treatment at 24 mg should be continued.

Table 4 Maintenance Dose of GSK1278863

Dose step	1	2	3	4	5	6	7	8
Dose level of GSK1278863 (once daily)	1 mg	2 mg	4 mg	6 mg	8 mg	12 mg	18 mg	24 mg
Number of GSK1278863 tablets taken	1 mg tablet ×1	2 mg tablet ×1	4 mg tablet ×1	6 mg tablet ×1	4 mg tablet ×2	6 mg tablet ×2	6 mg tablet ×3	6 mg tablet ×4

Table 5 Dose Adjustment Algorithm (GSK1278863)

Hgb (g/dL)	Hgb increase over 4 weeks (g/dL)	Treatment
>13.0	NA	Interrupt treatment until Hgb decreases to less than 12.0 g/dL Resume treatment at the one lower dose level (resume treatment at 1 mg once the one-step dose increase criteria are met, if interrupted at 1 mg)
12.0-13.0	NA	One-step dose reduction
10.0-<12.0	>2.0	One-step dose reduction
	≤2.0	Continue treatment at the current dose level
7.5-<10.0	>2.0	One-step dose reduction
	0.5-2.0	Continue treatment at the current dose level
	<0.5	One-step dose increase
<7.5	NA	Discontinue treatment permanently * and initiate another appropriate treatment

*: If an initial Hgb value is less than 7.5 g/dL, measurement will be repeated at the same study visit (using the same sample) to calculate the average. If the average meets the Hgb stopping criteria, study treatment will be discontinued.

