7.3. Efficacy

Efficacy will be assessed according to the Time and Event Table (Table 6).

Hgb concentrations measured by the central laboratory will be used for efficacy assessment (see Section 7.4.6.).

GSK will supply a point-of-care Hgb analyzer (HemoCue) to each site for rapid and convenient measurement of Hgb and to ensure consistency of Hgb measurements across all sites participating in the study. Hgb concentrations measured by HemoCue will be used for eligibility (Sections 5.1 and 5.2.), withdrawal (Section 5.4.), and dose adjustment criteria (Section 6.3.).

In addition, assessments of iron metabolism parameters used for efficacy assessment are outlined with specific procedures in Section 7.4.6.

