# 10.6.3. Efficacy

Hgb Values for Efficacy Analyses				
Central laboratory and HemoCue Hgb Values				
• For reporting purposes, central laboratory Hgb values will be used, unless otherwise specified. However, if a central laboratory Hgb value is missing, a corresponding non-missing HemoCue Hgb value, which is associated with the identical subject number and visit, will be used.				
Evaluable Hgb Values				
• Note that this will not be applicable for reporting summaries and figures, but applicable for reporting listings.				

 
Evaluable Hgb values will be based on on-therapy central laboratory and/or HemoCue Hgb values that are not taken within the 8 weeks following a transfusion or within the 8 weeks following a non-randomized ESA medication (except protocol-specified ESA treatment in screening period).
 
				
evaluable Hgb = 'N'.				

 
Blood Product Administration Date < Date of Hgb data ≤ Blood Product Administration Date + 56 (days)
 
				

corresponding HemoCue measurement) will be used. The figure will include Pearson's

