# 10.14.5. Efficacy Figures

Efficad	Efficacy: Figures							
No.	Populatio n	IDSL / TST ID / Example Shell	Title	Programming Notes	SAC			
Hgb								
2.1.	All Treated Subjects	EFF_F1	Plot of Mean Hgb (g/dL) and 95% CI for Change from Baseline over Time		Y			
2.2.	All Treated Subjects	EFF_F1	Plot of Mean Hgb (g/dL) and 95% CI for Change from Baseline over Time by Dialysis Status		Y			
2.3.	All Treated Subjects	EFF_F1	Plot of Mean Hgb (g/dL) and 95% CI over Time		Y			
2.4.	All Treated Subjects	EFF_F1	Plot of Mean Hgb (g/dL) and 95% CI over Time by Dialysis Status		Y			
2.5.	All Treated Subjects	EFF_F2	Figure of Number (%) of subjects with Hgb within the target range over time	Like Fig. 2.7.6.2.3.1-2 in NESP CTD 2.7.6	Y			
2.6.	All Treated Subjects	EFF_F2	Figure of Number (%) of subjects with Hgb within the target range over time by Dialysis Status		Y			
2.7.	All Treated Subjects	EFF_F3	Kaplan-Meier plot of Time (in days) to reach the lower target Hgb level $(10.0 \text{ g/dL})$		Y			
2.8.	All Treated Subjects	EFF_F3	Kaplan-Meier plot of Time (in days) to reach the lower target Hgb level (10.0 g/dL) by Dialysis Status		Y			
2.9.	All Treated Subjects	EFF_F4	Scatter plot of Hgb assessments: Central Laboratory vs. HemoCue		Y			
Dose A	djustment							
2.10.	All Treated Subjects	EFF_F5	Histogram of GSK1278863 Dose by Visit		Y			

Efficac	Efficacy: Figures							
No.	Populatio n	IDSL / TST ID / Example Shell	Title	Programming Notes	SAC			
2.11.	All Treated Subjects	EFF_F6	Subject Profiles of Hgb and Dose over Time		Y			
Iron Pa	arameters							
2.12.	All Treated Subjects	EFF_F1	Plot of Mean and 95% CI for Ferritin Change from Baseline over time		Y			
2.13.	All Treated Subjects	EFF_F1	Plot of Geometric Mean and 95% CI for Transferrin Saturation Percent Change from Baseline over time		Y			
2.14.	All Treated Subjects	EFF_F1	Plot of Geometric Mean and 95% CI for Hepcidin Percent Change from Baseline over time		Y			
2.15.	All Treated Subjects	EFF_F1	Plot of Mean and 95% CI for Serum Iron Change from Baseline over time		Y			
2.16.	All Treated Subjects	EFF_F1	Plot of Mean and 95% CI for Total Iron Binding Capacity Change from Baseline over time		Y			
Other								
2.17.	All Treated Subjects	EFF_F7	Scatter Plot of Change from Baseline in Hgb at Week 4 vs. Body Weight		Y			
2.18.	All Treated Subjects	EFF_F7	Scatter Plot of Change from Baseline in Hgb at Week 4 vs. Body Weight by Dialysis Status		Y			

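### The only planned comparison of central-laboratory and HemoCue Hgb is a scatter plot with Pearson's r, which cannot measure a systematic difference between the devices

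*SAP*

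**What the plan says.** The protocol gives the two measurements different jobs. In Protocol 7.3, "Hgb concentrations measured by the central laboratory will be used for efficacy assessment", while "Hgb concentrations measured by HemoCue will be used for eligibility" and also for withdrawal and dose adjustment. Protocol 6.3 sets dose changes "based on the HemoCue Hgb value measured every 4 weeks".

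The SAP lets one device stand in for the other. Under SAP 10.6.3, "if a central laboratory Hgb value is missing, a corresponding non-missing HemoCue Hgb value" from the same subject and visit is used. SAP 7.1.2 applies this to the primary analysis, SAP 8.1.3 applies it to the secondary Hgb analyses, and SAP 10.7.2.2 allows no other Hgb imputation. No adjustment for a device difference is stated.

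The comparison of the devices is in SAP 8.1.2: a scatter plot of the two Hgb measurements "will be produced along with Pearson's correlation coefficient". On the data, it says "All available pairs of Hgb (i.e. non-missing values in both from central laboratory and from the corresponding HemoCue measurement) will be used". The list of displays (SAP 10.14.5, Figure 2.9) has one entry, "Scatter plot of Hgb assessments: Central Laboratory vs. HemoCue". The SAP text specifies no mean difference, limits of agreement, concordance coefficient or identity line, and it does not say how several pairs from one subject are handled.

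**The concern.** Pearson's r measures how tightly the points follow some straight line. It does not measure how close they lie to the line of equality. If HemoCue read 0.5 g/dL high throughout, or 10% high, r would be the same as with no bias.

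Here the level difference is the quantity of interest. Subjects are steered towards 10.0 to 12.0 g/dL on one device and scored against 10.0 to 12.0 g/dL on the other. If target-range attainment is lower than hoped, the reader will want to know whether the dosing algorithm or a device difference explains it, and r cannot say. The same applies to the other central-laboratory endpoints with fixed cut-offs (time to 10.0, below 7.5, above 13.0 g/dL) and to whether a substituted HemoCue value is a fair stand-in.

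Pooling all visits also tends to raise r. Day 1 HemoCue Hgb is restricted to 8.0 to below 10.0 g/dL by the inclusion criteria, and treatment then spreads values upward. A wider spread raises r with no change in device error.

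**Working it through.** **Inputs from the documents.** Protocol 9.2.1: n = 20 at Week 4, SD 1.5 g/dL. Protocol 4.5: expected mean Week 4 rise 0.5 g/dL. Target range 10.0 to 12.0 g/dL, so 2.0 g/dL wide. Week 4 change categories between the two open-ended ones are 1 g/dL wide.

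**Assumptions, because the documents give no device-error figure.** Mean Hgb 10.5 g/dL; SD of true Hgb (s) 1.0 to 1.5; SD of paired differences (e) 0.3 to 0.4; constant HemoCue offset (b) 0 to 1.0 g/dL.

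**1. The plan's own figure.** Half-width = t(0.975, 19) × SD/√n = 2.093 × 1.5/√20 = 0.702 g/dL. This matches Protocol 9.2.1. It is used below only for scale.

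**2. What r responds to.** Let each device read true Hgb plus independent error of variance e²/2, and let HemoCue add b. Then r = s²/(s² + e²/2), and b does not appear.

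| s | e | r at any offset |
|---|---|---|
| 1.0 | 0.3 | 1/1.045 = 0.957 |
| 1.0 | 0.4 | 1/1.08 = 0.926 |
| 1.5 | 0.3 | 2.25/2.295 = 0.980 |
| 1.5 | 0.4 | 2.25/2.33 = 0.966 |

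Multiplying HemoCue by 1.1 (mean difference 0.1 × 10.5 = 1.05 g/dL) also leaves r unchanged. Spread, by contrast, does change r: with e = 0.3 and s = 0.5, r = 0.25/0.295 = 0.847, against 0.957 at s = 1.0.

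**3. What other statistics show (s = 1.0, e = 0.3).** At b = 0, 0.3, 0.5 and 1.0 the mean difference reads 0, 0.3, 0.5 and 1.0. Lin's concordance coefficient, 2s²/(2 × 1.045 + b²), reads 0.957, 0.917, 0.855 and 0.647; a simulation of 400,000 pairs agrees to within 0.001. At b = 0.5 the limits of agreement are 0.5 ± 1.96 × 0.3, or -0.09 to 1.09 g/dL.

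**4. Absolute-level results.** From the same simulations, over the four combinations of s and e, the share of values on which the devices disagree about being in 10.0 to 12.0 g/dL is:

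| Offset b (g/dL) | Disagree on in-target status |
|---|---|
| 0 (random error only) | 10% to 15% |
| 0.3 | 15% to 20% |
| 0.5 | 21% to 26% |
| 1.0 | 42% to 48% |

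An offset of 0.5 is a quarter of the target-range width (0.5/2.0).

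**5. Changes over time.** A constant offset cancels in a HemoCue-minus-HemoCue increase over 4 weeks. A proportional one does not cancel but rescales it: at 10%, a true rise of 2.0 reads as 2.2. The primary change uses central values at both visits, so HemoCue enters only by substitution. If exactly one of baseline and Week 4 is substituted, that subject's change moves by the full offset; at 0.5 this is half a response category. With k of 20 Week 4 values substituted and central baselines, the mean moves by k × b/20:

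| b (g/dL) | k = 1 | k = 4 |
|---|---|---|
| 0.3 | 0.015 | 0.06 |
| 0.5 | 0.025 | 0.10 |
| 1.0 | 0.05 | 0.20 |

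**6. Could this study estimate the offset?** With one pair from each of 20 subjects, the 95% CI half-width for the mean difference is 2.093 × e/√20, which is 0.14 at e = 0.3 and 0.19 at e = 0.4. An offset of 0.3 to 0.5 g/dL would be distinguishable from zero.

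**The case against.** The SAP plans a descriptive plot and prints r beside it. It sets no agreement criterion and draws no conclusion about interchangeability. Device comparison is not an objective or endpoint, and no test depends on it. A reader might infer that the sponsor intends to judge agreement by r, but the documents do not say so. This part of the objection stands.

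The plot shows the individual pairs, so a clear shift might be seen by eye. SAP Table 4 also marks HemoCue Hgb for individual listing, so the differences could be recovered from planned outputs. The mock shells are in separate documents (SAP 10.15), so an identity line cannot be ruled out. This is also fair, but an offset seen by eye has no estimate or interval, and the one summary number specified carries no information about it.

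A reader might also infer that every dosing threshold is shifted or that the primary endpoint is biased. Neither follows. The 4-week-increase rules in Protocol Table 5 compare HemoCue with HemoCue, so a constant offset cancels and only the absolute-level cut-offs are exposed. The primary change is affected only through mixed-device pairs. Central Hgb is scheduled at every treatment visit, and the rationale column of SAP Appendix 16 treats a missing Day 1 Hgb as not expected, so substitutions may be few. The duration of interruption for Hgb above 13 g/dL is derived from HemoCue (SAP 10.6.3) and so matches the dosing device.

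Finally, nothing in the documents suggests that HemoCue is biased. The central-laboratory target-range percentage is a valid description of Hgb achieved under HemoCue-guided dosing; substituted values aside, an offset affects its explanation rather than its validity.

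**Conclusion.** The point holds as a reporting weakness. The sponsor already plans to compare the devices, and the one statistic specified cannot show a constant or proportional difference. That difference is what a reader needs when interpreting the absolute-level central-laboratory endpoints under HemoCue-driven dosing, or when deciding how far to trust substituted values.

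The effect on the primary mean is small: 0.015 to 0.20 g/dL for assumed offsets of 0.3 to 1.0 g/dL and 1 to 4 of 20 Week 4 values substituted, against a planned half-width of 0.702 g/dL. The effect on in-target classification is larger: at an assumed 0.5 g/dL, disagreement between devices rises from 10% to 15% up to 21% to 26%. All these sizes rest on assumed offsets, error SDs and substitution counts. They show what r would miss, not that an offset exists. The documents do not support a stronger claim that the primary result or the dosing is compromised.

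**What to change.** In SAP 8.1.2, on the same pairs, add the mean paired difference (HemoCue minus central) with its 95% CI and the 95% limits of agreement. Allow for repeated pairs per subject, for example by a subject random effect on the differences. Add a difference-versus-mean plot, which would also reveal a proportional difference, or at least draw the identity line on Figure 2.9. Keep r only as a supplement. A footnote with the number of substituted Hgb values at each visit would let the reader size the effect on the primary mean.

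The cost is a sentence or two in the SAP and one extra figure or table from data already collected. No endpoint, dosing rule or data collection changes.
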